4.0 Risks and Benefits

Potential risks of each of the two arms of the study include bleeding, infection, implant exposure, implant malposition, seroma, delayed wound healing, mastectomy flap necrosis, and capsular contracture. This study may involve unpredictable risks to the participants.

There may be no benefits to participants in the study.

5.0 Study Design

This is a prospective, randomized-to-procedure, controlled, blinded-to-esthetic evaluator trial. Information recorded and evaluated will include:

Population Variables -

- age
- body mass index (BMI)
- breast size
- past medical history
- smoking history
- tumor size and location
- mastectomy surgeon
- mastectomy method

Operative Variables -

- plastic/reconstructive surgeon
- tissue expander
- tissue expander type
- quality of skin
- additional skin resection
- intraoperative fill volume
- method of lower pole expansion
- drains

Postoperative Variables -

- duration of drains
- chemotherapy
- radiation
- number of post-op visits
- time to first expansion
- number of expansions
- final fill volume
- time to exchange
- type and volume of implant placed
- contralateral procedures performed
- nipple (yes/no)

Outcome -

- infection
- seroma
- implant malposition
- capsular contracture
- hematoma
- histologic incorporation
- esthetic evaluation (photos, blinded evaluators)

6.0 Operative Technique

Intervention Arm:

After the mastectomy is performed, the pectoralis major muscle is elevated off the chest wall with electrocautery. After elevation superiorly and medially, the pectoralis major muscle is disinserted from the chest wall along its inferior border to the 3 or 9 o'clock position medially.

The skin envelope is evaluated. If the inframammary fold has been violated, sutures are used to secure it into its appropriate anatomic location. This is also done with the lateral breast skin.

Bioprosthetic mesh is then sewn into the inframammary fold and lateral chest wall. If Surgimend is used, then the 10 x 15 cm piece of fenestrated material is sewn to the fold, curved side along the fold, using a suture. If Alloderm (acellular dermal matrix) is used, a 6 x 12 cm piece or 6 x 16 cm piece is trimmed into a semicircle and sewn into the inframammary fold. The smooth side is placed against the implant.

The tissue expanders are then placed in the subpectoral/subbioprosthetic pocket. A drain is placed along the inferior border between the bioprosthetic mesh and the tissue expander. The superior border of the bioprosthetic mesh is closed to the inferior border of the pectoralis major muscle with a suture. An additional drain is placed in the subcutaneous pocket. Saline solution is then injected into the tissue expander to an appropriate fill volume.

Skin closure is performed.

7.0 Statistical Considerations

Primary endpoint

The study is designed to evaluate the overall complication rate post-tissue expander reconstruction surgery using different types of mesh. Patients who are eligible for the study will be equally randomized to the following arms: 1) Alloderm; 2) Surgimend. The primary endpoint, overall complication after tissue expander implant is defined as any of the following complications: seroma; infection; implant malposition; capsular contracture; and, hematoma.

Sample Size

Patients who are seen at MDACC for immediate breast reconstructive surgery after mastectomy will be enrolled to the study and equally randomized to the two arms when the tissue expander is implanted: 1) Alloderm; 2) Surgimend. The randomization will be stratified by surgeon in order to avoid confounding between surgeon and surgical method. A total of 398 patients will be enrolled with 199 patients for each arm. The information on overall complication observed after tissue expander implant and before

the permanent implant will be collected. The rate of overall complication for the patients using Alloderm mesh (arm 1) will be compared to the patients using Surgimend mesh (arm 2). With 199 patients in each arm the study will have 80% power to detect the difference in complication rate between 10% in the Alloderm mesh group and 20% in the Surgimend mesh group with a two-sided type I error rate of 0.05 (calculated by nQuery Advisor 7.0). The secondary objective is esthetic evaluation. The main question for the esthetic evaluation is whether the overall shape of the reconstructed breast is good. Evaluators who are blinded to the arm assignment information will grade the patients using a 5-point Likert scale (strongly disagree, disagree, somewhat agree, agree, strongly agree). Their scores will be averaged for each patient.

Analysis Plans

Patient information including age, BMI, smoking history, tumor size and location, breast size, mastectomy method, mastectomy surgeon, plastic reconstruction surgeon, quality of skin, tissue expander type, intraoperative fill volume, method of lower pole expansion, chemotherapy, and radiation therapy will be summarized. Outcome variables which include complications and scores for esthetic evaluation will be studied. Summary statistics including mean, standard deviation, median, and range will be provided for continuous variables (such as age and BMI) while frequency counts and percentages will be provided for categorical variables (such as smoking history and tissue expander type). The overall complication rate for each arm will be calculated along with the 95% confidence intervals. Fisher's exact test or the Chi-square test will be used to evaluate the association between two categorical variables. Cochran-Mantel-Haenszel test will be used to assess the association between treatment and outcomes by adjusting the stratification of surgeon's experience (≤ 3 years and >3 years). Logistical regression model will be used to assess the effect of patient variables on overall complication. For each question of the esthetic evaluation, an average score will be calculated for each patient based on the scores from all evaluators. Summary statistics for the scores including mean, standard deviation, median, and range will be calculated. The scores will be compared between the two mesh arms using Wilcoxon rank sum test.

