8.0 Data Collection

All population variables will be collected after enrollment in the study and prior to surgery. After the initial surgery, during which operative variables will be documented by the surgical team, patient data will be collected in clinic. At the postoperative week 1 visit, the patient will be assessed by the surgical team for incisional complications and mastectomy flap necrosis. At the postoperative week 2 visit, expansion will begin, absent complications preventing expansion. The patient will return to clinic for additional expansion, as determined by the a member of the surgical team, until the desired volume is reached. During each of these visits, the patient will be assessed for seroma and infection. After expansion, the patient will return in approximately 3 months for a preoperative visit, followed shortly by tissue expander exchange for a permanent implant. One to twelve months following implant exchange, 5 photographs

(standardized photographic views) will be taken and used for aesthetic evaluation (see Appendix D). Unique study numbers will be assigned to the photographs.

Population variables:

- age
- BMI
- breast size
- past medical history
- smoking history
- tumor size and location
- mastectomy surgeon
- mastectomy method

Operative Variables – These will be collected from the operative note or at the time of surgery:

- plastic/reconstructive surgeon
- tissue expander
- expander type
- quality of skin
- additional skin resection
- intraoperative fill volume
- method of lower pole expansion
- drains

Postoperative Variables – These will be recorded at clinic visits or retrospectively from clinic notes:

- duration of drains
- chemotherapy
- radiation therapy (out of study)
- number of post-op visits
- time to first expansion
- number of expansions
- final fill volume
- time to exchange
- type and volume of implant placed
- contralateral procedures performed
- nipple (yes/no)

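### Randomization is stratified by surgeon, but the CMH test of treatment adjusts for two-level surgeon experience: state the factor actually used and analyse by it

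*Combined protocol and SAP*

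**What the plan says.** Section 7.0, Sample Size, states the design factor and its purpose: "The randomization will be stratified by surgeon in order to avoid confounding between surgeon and surgical method". Patients are "equally randomized to the two arms when the tissue expander is implanted", so by context the surgeon meant is the reconstructive surgeon, although the text does not say so.

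Section 7.0, Analysis Plans, states the analysis factor: the "Cochran-Mantel-Haenszel test will be used to assess the association between treatment and outcomes by adjusting the stratification of surgeon's experience", in two levels (up to 3 years, more than 3 years). This is the only categorical test that the plan ties to treatment. The Fisher or chi-square sentence is generic and names neither treatment nor the primary endpoint. The regression sentence reads "Logistical regression model will be used to assess the effect of patient variables on overall complication". It may include surgeon, because the paragraph opens with a list of patient information containing "mastectomy surgeon, plastic reconstruction surgeon, quality of skin", but it names no treatment term.

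The design statement in Section 5.0 names no stratification factor. The variable lists in Sections 5.0 and 8.0 both include "plastic/reconstructive surgeon". Neither includes years of experience.

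**The concern.** The analysis paragraph does not present experience as an extra covariate. It speaks of the stratification of experience as if that already existed, but the design paragraph stratifies by individual surgeon. A reader cannot tell whether randomization was by surgeon and the analysis collapses it, or was by experience and the design paragraph is wrong.

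Adjusting for a coarser attribute of the surgeon is a valid analysis, and bias is not the issue. Two smaller things are at stake:

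- **Fit of test to design.** If randomization is by surgeon and surgeons differ in complication rate, collapsing to two levels leaves between-surgeon variation in the variance estimate. The test becomes mildly conservative and gives up some power. If randomization is by experience, the planned test is the matching one, and splitting further by surgeon can lose power.
- **An open choice.** The plan designates no primary test, so the choice of strata could be made after the data are seen.

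**Working it through.** **The plan's own figure.** Inputs from Section 7.0: 10% against 20%, two-sided alpha 0.05, power 80%, 1:1 allocation. With the unstratified, uncorrected two-proportion formula and p̄ = 0.15:

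n = [1.960·√(2·0.15·0.85) + 0.842·√(0.10·0.90 + 0.20·0.80)]² / 0.10² = (0.9897 + 0.4208)² / 0.01 = 198.96, or 199 per arm.

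The stated 199 per arm (398 in total) reproduces. It carries no allowance for, or benefit from, stratification.

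**The test compared under two sets of strata.** For stratum i with n_Ai and n_Bi patients per arm, n_i in total, m_i events and x_i events in arm A:

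CMH = [Σ(x_i − n_Ai·m_i/n_i)]² / Σ[n_Ai·n_Bi·m_i·(n_i − m_i) / (n_i²·(n_i − 1))]

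There is no continuity correction; the test rejects above 3.841.

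**Assumptions, because the documents give none.**

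- Surgeon volumes: 10 equal (39-40 patients each), 12 unequal (4 to 90), or 20 unequal (2 to 60).
- Normal surgeon effects on the logit scale with SD from 0 to 1.0. Intercepts are solved so that the marginal rates are 15%/15% (null) or 10%/20% (alternative).
- Experience correlated 0, 0.5 or 0.8 with the surgeon effect and split at the median surgeon.
- 100,000 simulated trials of 398 patients per scenario and hypothesis. Ranges below run over volume patterns and correlations.

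For scale, at a 15% overall rate, surgeons one SD either side of average have rates of about 9% and 21% at SD 0.5, and 4.5% and 26% at SD 1.0.

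**(A) Randomized by surgeon, permuted blocks of 4.**

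| Logit SD | Power, by-surgeon minus experience CMH (points) | Type I error, experience CMH |
|---|---|---|
| 0 | -0.3 to +0.1 | 4.9-5.1% |
| 0.25 | -0.3 to +0.2 | not tabulated |
| 0.5 | +0.1 to +0.7 | 4.6-4.9% |
| 0.75 | +0.7 to +1.4 | not tabulated |
| 1.0 | +1.4 to +2.3 | 3.9-4.4% |

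The by-surgeon CMH holds type I error at 4.8-5.1% throughout. The Monte Carlo standard error of the paired power difference is at most 0.06 points. Block size matters little: at correlation 0.5 and SD 1.0 the gain is +1.9 to +2.1 points with blocks of 2 and +1.7 to +2.0 with blocks of 8.

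**(B) Randomized by experience level.** The experience CMH has type I error 4.8-5.1% and power 80.3-81.7%. Switching to by-surgeon CMH changes power by -1.9 to -0.7 points at SD 0, -1.2 to +0.2 at SD 0.5, and +0.7 to +2.6 at SD 1.0.

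**Cross-check with simpler settings.** With 4 to 20 equal-volume surgeons, near-perfect balance within surgeon, experience unrelated to the surgeon effect, SD 0 to 1.0 and 20,000 trials per setting:

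| Strata | Power | Type I error |
|---|---|---|
| Surgeon | 80.4-84.7% | 4.8-5.2% |
| Two experience levels | 80.4-82.1% | 3.9-5.0% |
| None | 80.2-81.9% | 3.8-5.0% |

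The largest gap between the first two rows, with 20 surgeons at SD 1.0, is 84.7 − 82.1 = 2.6 points from the rounded figures (2.7 unrounded).

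**If the choice is left open.** Taking the smaller of the two CMH p-values after seeing the data would give type I error of at most about 5.4% under (A) and 6.8% under (B). The plan does not propose this; the figures only bound what an unsettled choice could cost.

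**The case against.** The strongest reply is that there may be no contradiction. CMH is a stratified test by definition, so the phrase about experience could describe only the analysis strata. Balance within surgeon gives approximate balance within experience level, so randomizing by surgeon and analysing by experience can coexist. The design paragraph is also the more explicit of the two and gives a reason, which makes randomization by experience the less likely reading. Next, the primary comparison may be the unstratified chi-square test, since the sample size reproduces without strata; the mismatch would then touch only a supportive analysis. Finally, the gain is under 1 point unless surgeons differ considerably, and everything that drives it is assumed.

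Much of this stands. The planned test is valid and keeps at least 80% power in every scenario examined. The smaller-p-value figures describe a hypothetical, and experience can be obtained once from surgeon identity, so its absence from the variable lists is weak evidence by itself. But neither alternative reading removes the point. Under by-surgeon randomization, both the experience-adjusted and the unstratified test are conservative when surgeons differ, and the text still does not say which test is primary. Matching the test to the randomization factor needs no extra patients.

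**Conclusion.** The concern holds as a point to consider. The two parts of Section 7.0 name different stratification factors, and nothing else in the document settles which was used. There is no confounding and no type I error inflation from either test used alone, and the sample size is unaffected.

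If randomization is by surgeon, the by-surgeon test is worth roughly nothing when surgeons are alike, 0.1 to 0.7 power points at logit SD 0.5, and 1.4 to 2.3 at SD 1.0, which is a large spread. If randomization is by experience, the by-surgeon test can cost up to 1.9 points when surgeons are alike. These sizes depend on the assumed number of surgeons, volumes, block size and spread. That the better test depends on which paragraph is correct does not depend on the exact values.

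**What to change.** State the factor actually used to randomize, correct whichever paragraph is wrong, and name one primary test of overall complication before the arms are compared.

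- **If it is surgeon:** say that this means the reconstructive surgeon, if so, and make the CMH test stratified by surgeon primary. Fix any rule for pooling very-low-volume surgeons before complications are compared by arm. Keep the experience-adjusted CMH as a sensitivity analysis.
- **If it is experience:** correct the Sample Size paragraph, including its stated purpose. Record each surgeon's experience at a fixed time, for example at that surgeon's first randomized patient. Make the CMH test already in Analysis Plans primary.

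Cost: no change to 398 patients. The by-surgeon test needs only surgeon identity, already listed in Sections 5.0 and 8.0. Any use of experience, including the test now planned, needs years of experience to be obtained once per surgeon. The downside of the by-surgeon test is that strata with no events or only one arm contribute nothing. With no between-surgeon spread this cost at most 0.3 power points with blocks of 4 and 0.6 with blocks of 8. With 20 surgeons and blocks of 4, pooling surgeons with fewer than 8 patients cut the 0.3 to under 0.1 (power 80.2% by surgeon, 80.5% pooled, 80.6% by experience).

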1.0 Background

For years, plastic surgeons have struggled with two opposing goals in tissue expander breast reconstruction: protecting the implant from exposure under a thin mastectomy skin flap; and, creating an esthetically appealing breast with a full lower pole. For many surgeons, these two goals seemed mutually exclusive. Protecting the implant meant placing it completely underneath the pectoralis major and serratus muscle, forcing the implant into an unnaturally high position. On the other hand, releasing the pectoralis major muscle allows the implant to sit within the mastectomy skin flap, but exposes the lower pole of the implant to a purely subcutaneous plane.

In recent years, there has been a proliferation of bioprosthetic mesh products. Some of these products found their way into breast reconstruction^{1,2,3,4}. Plastic surgeons began using bioprosthetic mesh as a sling to allow the pectoralis major muscle to be released and then reconnected to the inframammary fold. This hammock effect protects the implant from the subcutaneous plane, takes tension off of the precarious mastectomy flap skin, and allows better control of the inframammary fold and lateral border of the breast. The additional thickness of the bioprosthetic mesh also helps to even out the thickness of the tissue overlying the implant, which is skin and muscle above and skin and mesh below^{6,7,8}.

As experience with reconstruction using bioprosthetic mesh has grown, increasing evidence suggest that mesh products may be associated with increased complication rates, particularly seroma and infection, potentially effecting not only the reconstruction, but the course of cancer treatment by delaying chemotherapy or interfering with radiation protocols^{5,9,11}. Because the mesh products consist of extracellular matrices that are created from different source materials (human, pig, cow), and are processed differently, it is logical to conclude that complication profiles, and possibly esthetic outcome, differ from product to product.

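### The logistic model leaves its covariates undefined and does not name the arm, and no adjusted mesh effect with a confidence interval is planned; a short supportive model would supply one at wording-only cost

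*Combined protocol and SAP*

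**What the plan says.** The Analysis Plans paragraph of Section 7.0 (combined protocol and SAP) handles overall complication in four ways:

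- a rate with a 95% confidence interval for each arm;
- Fisher's exact or chi-square tests for pairs of categorical variables;
- a Cochran-Mantel-Haenszel (CMH) test of treatment and outcome, with strata for surgeon's experience of up to three years or more than three years;
- a regression described in full as "Logistical regression model will be used to assess the effect of patient variables on overall complication".

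The last item has no covariate list, no selection rule and no mention of the arm.

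The same paragraph opens with 14 items of patient information. The list ends with "method of lower pole expansion, chemotherapy, and radiation therapy will be summarized", so its only stated use is descriptive.

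Section 7.0 also has patients "equally randomized to the two arms when the tissue expander is implanted", with randomization stratified by surgeon. Section 8.0 has the population variables, among them age, BMI, breast size and smoking history, collected after enrollment and before the operation. It puts chemotherapy and radiation under its postoperative heading, as Section 5.0 does.

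**The concern.** Two things are at stake.

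First, the plan has no adjusted estimate of the mesh effect. The CMH analysis is stated as a test, and it uses a two-level experience factor although the randomization factor is surgeon. The only regression on the primary endpoint does not mention the arm. Baseline data that could sharpen and support the mesh comparison are collected but have no stated role in it.

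Second, the undefined term lets in an unsound model. The nearest list of patient information includes two postoperative treatments. The Background (Section 1.0) says complications may affect cancer care by "delaying chemotherapy or interfering with radiation protocols". If that happens, part of any association between these treatments and complications runs from the complication to the treatment. A coefficient reported as a risk factor would then mislead. The same list is also long for the number of events expected.

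**Working it through.** **1. The plan's own figure.** The inputs, all from Section 7.0, are a "difference in complication rate between 10% in the Alloderm mesh group and 20% in the Surgimend mesh group", a "two-sided type I error rate of 0.05", and the statement that "the study will have 80% power". With pooled variance under the null and no continuity correction:

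n per arm = [1.960 × √(2 × 0.15 × 0.85) + 0.842 × √(0.10 × 0.90 + 0.20 × 0.80)]² / 0.10² = (0.990 + 0.421)² / 0.01 ≈ 199

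Power at 199 per arm is 80.0%. The stated size reproduces: "A total of 398 patients will be enrolled with 199 patients for each arm".

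**2. Expected events.** 199 × 0.10 + 199 × 0.20 = 59.7.

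**3. Events per variable, by reading of the undefined term.**

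| Reading | Terms | 59.7 / terms |
|---|---|---|
| Population group of Sections 5.0 and 8.0 | 8 | 7.5 |
| Summarized list without chemotherapy and radiation | 12 | 5.0 |
| Summarized list, one term per item | 14 | 4.3 |
| Same, tumor size and location split | 15 | 4.0 |
| Same list with factors in levels (assumed) | 20 | 3.0 |
| Same list with factors in levels (assumed) | 25 | 2.4 |

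The figure also moves with the true rates. With 14 terms it is 39.8 / 14 = 2.8 if both arms are at 10%, and 79.6 / 14 = 5.7 if both are at 20%.

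**4. What many terms would do.** This is an illustrative simulation with 398 patients, an event rate of about 13%, independent covariates, one true odds ratio of 1.5 and 1,500 replicates per setting. All inputs except the 398 are assumptions.

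| Terms | Inflation of the true log odds ratio | Chance of at least one false-positive covariate at 0.05 |
|---|---|---|
| 5 | about 1% | 18% |
| 15 | about 6% | 53% |
| 25 | about 12% | 75% |

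Most of the last column is plain multiplicity. With 14 null covariates, 1 − 0.95^14 = 51%.

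**5. Where the listed items fall in time.** Under the groupings of Sections 5.0 and 8.0, seven of the 14 items are population variables, five are operative and two (chemotherapy and radiation) are postoperative. Section 7.0 takes complications from expander placement to the permanent implant. Section 8.0 does not ask when chemotherapy or radiation occurred relative to a complication. On the documents alone, the direction of an association could not be settled.

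**6. The proposed model.** Arm plus three one-degree-of-freedom covariates gives 59.7 / 4 = 14.9 events per parameter. Arm plus four gives 59.7 / 5 = 11.9, and arm plus five gives 59.7 / 6 = 9.95. These figures exclude surgeon. The number of surgeons is not stated. As an assumption, six surgeons entered as indicators would add five terms (59.7 / 10 = 6.0), and eleven would add ten (59.7 / 15 = 4.0). That favors a stratum or random effect over indicators.

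**7. Gain from adjustment.** Simulated power for the arm effect, with four baseline covariates, marginal rates of 10% and 20%, and 3,000 replicates. The documents do not give the strength of the covariates, so a range is assumed.

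| Assumed SD of combined covariate effect on the logit | Unadjusted | Adjusted |
|---|---|---|
| 0 | 80.5% | 80.5% |
| 0.5 | 80.2% | 81.4% |
| 0.8 | 80.3% | 83.9% |
| 1.0 | 81.0% | 85.2% |

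The gain is 0 to about 4 points.

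**The case against.** The strongest reply is that the plan does not say what a critical reader may take from it. Several stronger readings are tempting, and the documents do not support them.

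- *The model will use the 14 items.* The text says only that they are summarized. Patient variables could equally mean the eight population variables, all collected before surgery. Nor does the sentence say that everything enters one joint model. The 4.3 figure and the chemotherapy and radiation point are therefore conditional.
- *The arm is left out on purpose.* No covariate is named at all, so this is silence and not a stated exclusion.
- *The mesh comparison is unadjusted.* It is adjusted, by the CMH test. What is missing is an adjusted estimate with an interval.
- *Every post-allocation variable gives a biased coefficient.* Fill volume is set after the mesh is sewn in (Section 6.0), but at the operation and so before any postoperative complication. It is unsuitable when the target is the total effect of mesh, but a complication cannot cause it. For chemotherapy and radiation the risk depends on coding and timing, which are not given.

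It can also be said that Section 2.0 has no risk-factor objective, and that the regression touches neither the primary test nor the sample size. All of this stands, and it limits the size of the point. It does not remove it: on any reading the covariates are not prespecified, and no adjusted arm effect is planned.

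**Conclusion.** The concern holds as a low-cost improvement, not as a flaw in the primary comparison. Without conditions, the regression's covariates are undefined, the arm is not named, and the only adjusted mesh analysis is a two-level CMH test with no specified estimate or interval.

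Conditional on the summarized list being the covariate set, the model would have about 4.3 events per variable at the design rates (2.8 to 5.7 with both arms at 10% or both at 20%). It would also contain two treatments whose coefficients could not be read as effects on complications.

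A reader might infer that the trial's main result is at risk or that adjustment brings a large gain. Neither follows. The 199 per arm reproduces and the planned test is unaffected. The gain is roughly 0 to 4 power points and rests wholly on assumed covariate strength. The main benefit is a prespecified adjusted effect with its interval.

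**What to change.** Add to the Analysis Plans paragraph of Section 7.0 a supportive logistic model of overall complication with:

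- randomized arm;
- a short fixed list of covariates collected before surgery, for example age, BMI and breast size. Smoking history is optional, because Section 3.0 excludes current smokers and its range is restricted;
- surgeon as a stratum or random effect, matching the randomization.

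Report the adjusted arm effect with its 95% confidence interval, labelled as support for the primary comparison. State that an adjusted odds ratio is conditional on the covariates and need not equal the crude one. Rates of 10% and 20% give a crude ratio of (0.20 / 0.80) / (0.10 / 0.90) = 2.25. In the simulation with SD 1.0 the conditional log odds ratio was 0.914, a ratio of about 2.5.

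Keep chemotherapy, radiation and other post-allocation variables out of this model. Summarize them by arm, or analyze them separately under an exploratory label. If a wider analysis of patient factors is retained, define patient variables and mark that analysis exploratory too.

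The cost is wording only: the covariates are already collected, and no patients or visits are added. The downside is that chemotherapy and radiation are not estimated as risk factors in this model. The primary test and the sample size stay as they are.
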